Study Protocol

Effect of Locally-Applied Simvastatin on Clinical Attachment Level and Alveolar Bone in Periodontal Maintenance Patients

[figure not shown]
NCT: 03452891

March 3, 2022

Patient Population

This one year, randomized, and double-masked clinical trial was conducted from March 2019-December 2020. Fifty patients, who were receiving periodontal maintenance therapy at the University of Nebraska Medical Center (UNMC) College of Dentistry were screened and identified by faculty and investigators involved in this study (RR, AK, MC and HR). Assessment included a review of medical and dental histories and previous oral hygiene and periodontal charting. Inclusion criteria for the study included subjects between the ages of 40-85 years, a periodontal diagnosis of advanced chronic periodontitis (stage III-IV, Grade B (Tonetti et al. 2018)), one quadrant with at least three posterior teeth and one 6-9 mm periodontal pocket with a history of BOP and no radiographic vertical bony defect ≥ 1.5 mm, overall good systemic health, and a history of regular PMT. Exclusion criteria consisted of subjects with systemic diseases that significantly affect periodontal inflammation and bone turnover (e.g., chronic use of steroids or non-steroidal anti-inflammatory drugs, estrogens, bisphosphonates, calcitonin, methotrexate, antibiotics, >325 mg aspirin/day), surgical periodontal therapy within the past year, and pregnant or breast-feeding females. Patients who met the inclusion criteria had the protocol explained and had all questions answered prior to obtaining consent.

Figure 1: Study Design Flowchart

Data Collection

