For the experimental interproximal treatment sulcus, BOP was considered present at baseline if at least one buccal or lingual interproximal site had the condition present. The follow-up variables for BOP were determined as follows: if the patient started without BOP and ended without BOP or showed a reduction (i.e. presence of BOP at baseline to absence of BOP at 12 months), that patient was considered to have a good outcome. If the patient began with BOP and showed no improvement or they developed BOP, that patient was considered to have a poor outcome. Associations between categorical variables were assessed using Chi-Square tests, or Fisher's exact tests when expected cell counts were low. Medians and inter-quartile ranges (IQRs; the range of the middle 50% of the data (25th percentile, 75th percentile)) were calculated for each treatment condition, and Wilcoxon Rank Sum tests were used to examine differences in distributions of BOP between the two treatment conditions (i.e. SIM/MCL or MCL) for baseline BOP values. For the change in BOP outcome, logistic regression models were used, which included group and adjusted for worst side. Adjusted odds ratios are presented with 95% confidence intervals.

Descriptive statistics for raw GCF and RT-PCR continuous data are given as medians and interquartile ranges (IQRs, representing the range of the middle 50% of the data). For analysis, data was log transformed due to skew.

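### The 'change in BOP' outcome is, on a binary reading, absence of BOP at 12 months, so its odds ratio should not be reported as change (minor, secondary outcome)

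*Combined protocol and SAP*

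**What the plan says.** All of the outcome and model text is in the Statistical analyses section of the combined protocol and SAP.

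- **Presence rule, given for baseline only:** "BOP was considered present at baseline if at least one buccal or lingual interproximal site had the condition present".
- **Good outcome:** "if the patient started without BOP and ended without BOP or showed a reduction", where reduction is explained as "presence of BOP at baseline to absence of BOP at 12 months".
- **Poor outcome:** "If the patient began with BOP and showed no improvement or they developed BOP, that patient was considered to have a poor outcome".
- **Model:** "For the change in BOP outcome, logistic regression models were used, which included group and adjusted for worst side". The section does not define worst side. Adjusted odds ratios with 95% confidence intervals are reported.
- **Baseline BOP between arms:** a separate comparison, in which "Wilcoxon Rank Sum tests were used to examine differences in distributions of BOP between the two treatment conditions".

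Elsewhere, Patient Population requires a history of BOP at the pocket, not BOP at the baseline visit. Data Collection records BOP at six sites per tooth, and Treatment Protocol repeats the clinical measurements at 12 months. The primary clinical outcome is change in clinical attachment level (CAL), so BOP is secondary.

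**The concern.** An odds ratio labelled as change in BOP will be read as saying how much more often bleeding improved in one arm than in the other. If the coding ignores where each patient started, the odds ratio says something else. It puts patients who never bled together with patients whose bleeding stopped and calls both a success.

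A second, separate question is why the model does not use baseline BOP, which is already recorded and likely to be related to 12-month BOP. In a trial of about 44–50 patients, the arms can differ at baseline by chance. The stated between-arm test could reveal such a difference but would not adjust the odds ratio for it.

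**Working it through.** **Inputs from the document.** The classification rules and model terms are quoted above. The sample size is 22 per group, and "Fifty patients, who were receiving periodontal maintenance therapy" were screened and identified, so 44–50 patients are used below. The 22 was set for CAL (1.0 mm difference, SD 1.1 mm, two-sided 0.05). A noncentral-t calculation gives 83.8% power at 22 per group, consistent with the stated minimum of 80%. BOP has no design figure to reproduce.

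**Step 1: the coding.** This takes BOP as present or absent and applies the baseline presence rule at 12 months.

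| Baseline | 12 months | Class |
|---|---|---|
| absent | absent | good |
| present | absent | good |
| present | present | poor |
| absent | present | poor |

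In all four rows, good is the same as absent at 12 months. Baseline status never alters the class.

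A constructed example, deliberately extreme, shows the consequence. In arm A, 25 of 25 bleed at baseline and 15 resolve. In arm B, 15 of 25 bleed, 5 of those resolve, and the 10 non-bleeders stay free. Both arms have 15/25 good, so the odds ratio is 1.0. Resolution among bleeders is 15/25 = 60% against 5/15 = 33%.

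**Step 2: how far the label misleads.** Let p be baseline prevalence, and let r0 and r1 be the control-arm 12-month BOP risks for patients without and with baseline BOP. All three are assumed. The share of good outcomes from patients with no baseline BOP is

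(1−p)(1−r0) / [(1−p)(1−r0) + p(1−r1)].

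| p | r0 = 30%, r1 = 70% | r0 = 40%, r1 = 60% |
|---|---|---|
| 50% | 70.0% | 60.0% |
| 70% | 50.0% | 39.1% |
| 85% | 29.2% | 20.9% |
| 95% | 10.9% | 7.3% |

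For example, at p = 85%: 0.15×0.7 / (0.15×0.7 + 0.85×0.3) = 0.105/0.360 = 29.2%.

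**Step 3: chance baseline imbalance.** The SD of the difference in baseline prevalence is √(2p(1−p)/n). Over p = 50–95% it is 15.1 to 6.6 points at n = 22 and 14.1 to 6.2 at n = 25. A 1 SD imbalance, split evenly about p, moves a true null odds ratio to 1.056–1.273 (n = 22) or 1.052–1.254 (n = 25). This is ordinary sampling error, which the confidence interval covers.

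As a size check, take baseline BOP of 20/25 against 16/25 and 12-month BOP of 10/25 in both arms. The odds ratio without baseline BOP is 1.00. Refitting with baseline BOP, over all cell fills with a fitted baseline odds ratio of 1.3–6.4, gives 1.04–1.32 (p 0.66–0.94). The inference does not change.

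**Step 4: power.** Simulations used 40,000 null and 40,000 alternative trials per scenario, a conditional odds ratio of 0.25, and both models calibrated to exactly 5%. Worst side was simulated as a binary term unrelated to outcome. Adding baseline BOP changed power as follows:

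- Largest gain: 0.445 to 0.489, or +4.4 points (n = 22, p = 50%, 40-point risk gap).
- Largest loss: 0.570 to 0.560, or −1.0 point (n = 22, p = 85%, 20-point gap).
- Largest gain at p = 85% or more: 0.583 to 0.606, or +2.3 points (n = 25, p = 85%, 40-point gap).

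**Step 5: can the baseline coefficient be estimated?** It cannot if there are no baseline non-bleeders or if all of them share one outcome. With N patients and risk r0 in both arms, that probability is

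(p + (1−p)r0)^N + (p + (1−p)(1−r0))^N − p^N.

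For N = 44–50 and r0 = 30% or 40%, it is 51–62% at p = 95% and 5–14% at p = 85%. The group odds ratio can still be estimated in those cases.

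**The case against.** The strongest reply is that little follows from this. The classification is set out in full just before the model, so a careful reader can see that patients who never bled count as good. The randomised comparison is valid, BOP is not primary, and a baseline imbalance would show in the planned between-arm test. All of that stands, and it limits the point to a minor one.

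Four further objections have force:

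- **The coding is not fully explicit.** A patient who goes from two bleeding sites to one is not clearly assigned, because poor requires no improvement. The bracketed explanation of reduction as presence to absence favours the binary reading, but the identity in Step 1 depends on it.
- **Worst side is undefined.** If it reflects a baseline clinical reading, it might carry some baseline information and the power comparison would differ. Nothing in the text identifies it as baseline BOP.
- **The sizes are assumed.** Selecting deep pockets with a history of BOP may make baseline prevalence high, and the 60–70% share needs a prevalence of only 50%. The text does provide for patients who started without BOP.
- **Adjustment changes the estimand.** Odds ratios are non-collapsible, so the adjusted value is conditional on baseline BOP and need not equal the unadjusted one.

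A reader might infer that the missing covariate is the reason the odds ratio does not describe change. It is not; the coding is. Adding baseline BOP would still leave patients who never bled counted as successes. A reader might also infer that the comparison is biased or underpowered for want of the covariate. Randomisation rules out the first, and Step 4 gives little support to the second.

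**Conclusion.** The point holds as a minor one on a secondary outcome. On the binary reading, the outcome called change in BOP is absence of BOP at 12 months, and its odds ratio compares that absence between arms. It should not be reported as change or improvement. How misleading the label is depends on baseline prevalence, which the document does not give: 60–70% of control-arm good outcomes could not be improvements at 50% prevalence, falling to 7–11% at 95%. If every patient bled at baseline, the outcome would equal resolution and the label would be accurate.

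The absence of a baseline BOP term is a separate and smaller matter. It leaves chance imbalance unadjusted but causes no bias, and the expected gain in precision from adding the term is small. These conclusions assume that the baseline presence rule also applies at 12 months. The sizes rest on the assumed risks in Step 2 and, for power, on a worst-side term unrelated to outcome.

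**What to change.** 1. Name the outcome absence of BOP at 12 months. Define it as no interproximal site of the experimental sulcus bleeding, so that one remaining bleeding site counts as present. This also settles the two-sites-to-one case.
2. Report the stated model and, beside it, the same model with baseline BOP (present or absent at the experimental sulcus) added. State that the adjusted odds ratio is conditional on baseline BOP.
3. Label the adjusted model as a later addition. The document is dated March 2022, says that the "clinical trial was conducted from March 2019-December 2020", and describes the analyses as already performed.
4. State a fallback: if baseline non-bleeders are absent or all share one outcome, use Firth-penalised logistic regression or report only the stated model.

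The cost is a changed label and one covariate already collected. The downside is one extra parameter in a model of about 44–50 patients, with a possible power loss of about 1 point.

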Clinical measures and gingival crevicular fluid (GCF) collection were collected by one of three calibrated dentists (RR, AK, and RH). During GCF collection, experimental site (6-9 mm interproximal pocket with no vertical bony \geq 1.5 mm, and history of bleeding on probing) was isolated with cotton rolls and gently dried with gauze. Supragingival plaque was removed from the test with a dental explorer. For GCF collection, an absorbent paper strip (PerioPaper Strips, Oraflow, Hewlett, NY) was inserted into the facial and lingual/palatal sulcus of the experimental site (Figure 2). After 30 seconds, the paper strips were immediately placed into a sterile vial and frozen at -80°C until further analysis. Strips contaminated by blood were discarded and were retaken after two minutes. Next, supragingival plaque, recession, probing depths, and bleeding on probing (BOP) within 30 seconds were recorded on 6 sites (MF, F, DF, ML, L, DL) on the experimental tooth and adjacent tooth.

Treatment Protocol

After the clinical data and GCF collection was completed, the investigator involved with data collection left, and the surgical / drug application phase of treatment was completed by a single clinician (LK, MB) and assistants (MC, LA) not involved with clinical measurements as described previously (Jasa et al. 2020). Following administration of local anesthesia to the experimental site, a #12B blade was used to reflect both the facial and lingual/palatal papilla including in the experimental 6-9 mm interproximal pocket. Interproximal soft tissue was removed to allow access to the root. To measure activation of gene markers of inflammation and bone turnover, an approximately 2x2x2 mm piece of the interproximal tissue was placed in a sterile vial of 1.5 mL RNA*later* solution (ThermoFisher Scientific, Waltham, MA) (Figure 3) and frozen at -20°C until further analysis. Scaling and root planning was performed interproximally on the test site and on the adjacent interproximal tooth surface. Verification

of a clean and smooth root surface was done using an 11/12 explorer and the Perioscope (Perioscopy Unit, Zest Dental Solutions, Carlsbad, CA) by the clinician (Figure 4).

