After mechanical therapy was completed, the unmasked clinician (LK or MB) randomly assigned patients to test simvastatin in methylcellulose (SIM/MCL) or control (MCL) groups. The root surface was etched for 2 minutes with ethylenediaminetetraacetic acid (EDTA, Pref-Gel, Straumann, Andover, MA) followed by irrigation with sterile saline. SIM and MCL were prepared by local compounding pharmacy (Pharmacy Solutions Lincoln, NE) and mixed immediately prior placement to achieve 2.2 mg simvastatin (SIM) suspended in 0.15 ml methylcellulose gel (MCL) (test group) or 0.15 ml of methylcellulose gel alone (control group)(Figure 5).

Gels were placed at the base of the pocket and deposited up the interproximal root surface of the experimental tooth (Figure 6). The papilla were re-approximated under pressure and sealed using cyanacrylate (PeriAcryl, Glustitch, Delta, BC, Canada). Routine periodontal maintenance therapy (PMT) then was completed by MC or LA, including full mouth periodontal charting, debridement, and root planing of inflamed pockets avoiding the experimental area. Patients were instructed to avoid brushing and flossing of the experimental site for 6 weeks. They were dispensed Listerine (Johnson & Johnson Consumer, Inc., New Brunswick, New Jersey) and instructed to be used twice a day for 30 seconds for 6 weeks. Patients were asked to return for postoperative visits after 2 and 6 weeks along with PMT recalls at 3, 6, 9, and 12 months. GCF collection was repeated at 2- weeks and 12-month PMT visits and clinical measurements were repeated at 12 months (Figure 7) by one of the three calibrated examiners (AK, RR, and HR). Collection of approximately 2x2x2 mm interproximal tissue was repeated at 2 weeks by either LK or MB. During the 6-week follow up, patients were given Gel-Kam® preventative treatment gel (Colgate Oral Pharmaceuticals, NY, NY) and a GUM® Proxabrush® (Sunstar Americas, Inc., Schaumburg, IL) and patients were instructed to brush the experimental site twice a day using the provided

interproximal brush. Participants were questioned about adverse events at 2-weeks and 6-months, and 12-months PMT visits.

Figure 2: Baseline GCF Sample

Perioscope use

Figure 3: Baseline Interproximal tissue

Figure 4:

Figure 5: Mixing SIM & MCL

Figure 6: Placement of SIM

Figure 7: 12-months post-therapy

Analysis of GCF samples

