General estimating equations were run with each measure of interest as the outcome, and each model included the variables (analyte) group and time, as well as the interaction between group and time to assess if change over time differed by group. If the interaction was not significant, main effects models were run. P-values for post hoc comparisons were adjusted using simulation methods. Pearson correlations were also run to assess for association between GCF and interproximal tissue samples at a given time point. Clinical attachment level (CAL) change between baseline and 12-months was the primary clinical outcome measure for this clinical trial. For change in CAL baseline CAL values were subtracted from 12 months CAL value, and difference scores were plotted against GCF and rt-PCR measures at two weeks (i.e. > negative values indicate reduction in clinical attachment loss). Associations between change in CAL and measures at 2-weeks were assessed using Pearson correlations. All analyses were performed using SAS software version 9.4 (SAS Institute Inc., Cary, NC).

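### Secondary GCF and tissue models: the main-effects fallback gives a group term that averages in the pre-randomisation visit, so for tissue it is half the drug effect

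*Combined protocol and SAP*

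**What the plan says.** The Statistical analyses section uses generalised estimating equations on log-transformed GCF and RT-PCR measures. Each model has group and time, "as well as the interaction between group and time to assess if change over time differed by group". The next step depends on that test: "If the interaction was not significant, main effects models were run". On multiplicity it adds: "P-values for post hoc comparisons were adjusted using simulation methods". It names no baseline covariate, no constraint on baseline means, no working correlation and no significance level for the interaction. It does not say how the group term of the reduced model is to be read.

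The order of events is in the Treatment Protocol section. The surgical and drug phase began "After the clinical data and GCF collection was completed". During surgery a "piece of the interproximal tissue was placed in a sterile vial". Only after mechanical therapy had the unmasked clinician "randomly assigned patients to test simvastatin in methylcellulose (SIM/MCL) or control (MCL) groups". On follow-up: "Collection of approximately 2x2x2 mm interproximal tissue was repeated at 2 weeks", and "GCF collection was repeated at 2- weeks and 12-month PMT visits". Tissue therefore has two time points and GCF has three, and in both the first precedes randomisation.

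**The concern.** In a randomised comparison with a pre-treatment visit among the time levels, the treatment effect is the difference between groups in their change from baseline, which is the interaction. Removing the interaction forces one group difference on all visits, including a visit where the drug cannot have acted. The remaining group coefficient is a weighted average of zero and the follow-up effects. It also carries any chance baseline difference.

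If the drug changes an analyte but the interaction misses significance, the only group estimate the plan then provides is too small. If that term is read as a drug effect, each analyte also gets a second test. The biomarker results are the trial's evidence on mechanism, covering nine GCF analytes and every tissue gene, so they could be misstated.

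**Working it through.** **Inputs.** The documents give 22 per group, a CAL difference of 1.0 mm, an SD of 1.1 mm and two-sided alpha 0.05 (Statistical analyses). They give no effect size or within-patient correlation r for any biomarker. I assume complete data, equal variances, r = 0.5 (range 0.3-0.7), and a true effect of 0.60 SD or 1.0/1.1 = 0.91 SD. The second is the CAL planning effect, used only as a larger reference value.

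**1. The plan's own figure.** The exact t-test calculation for CAL needs 21 per group (power 82.0%); 22 gives 83.8%. The stated 22 for at least 80% power is confirmed. It serves here only to fix n.

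**2. Baseline must be a time level.** Tissue has only baseline and 2 weeks, so without baseline there is no time factor. For GCF this is an inference: the same model is described for every measure, its purpose is change over time, and no baseline covariate is named.

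**3. Weights in the group term.** With working correlation matrix R, the visit weights are w = 1'R⁻¹ / (1'R⁻¹1).
- Tissue: w = (0.5, 0.5) at any r, so 0.5 × 0 + 0.5 × 0.60 = 0.30 SD. At 0.91 SD it is 0.45 SD.
- GCF, independence or exchangeable: w = (1/3, 1/3, 1/3). A 0.60 SD effect at both follow-ups gives 0.40 SD; at 2 weeks only, 0.20 SD.
- GCF, AR(1): w = (0.370, 0.259, 0.370) at 0.3 and (0.435, 0.130, 0.435) at 0.7. The fractions are 0.63 to 0.57 for a sustained effect and 0.26 to 0.13 for a 2-week-only effect.

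GEE fits to 1,000 simulated tissue data sets at 0.60 SD and r = 0.5 gave a mean group term of 0.305 overall and 0.307 where the interaction was non-significant. Selection on that test therefore does not restore the effect. Random loss of 10% or 20% of 2-week samples lowered the overall mean to about 0.29 or 0.24.

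**4. How often, and with what consequence (tissue).** Standard errors in SD units at r = 0.5:
- interaction: √[2(1−r) × 2/22] = 0.30
- mean of the two visits: √[(1+r)/2 × 2/22] = 0.26

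At 0.60 SD the group term is off target by 0.30/0.26, or about 1.15 standard errors, which gives coverage near 80%. The simulation (40,000 replicates) used a t-test on change for the interaction, a t-test on the visit mean for the group term, and ANCOVA at 2 weeks:

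| r = 0.5 (range for r 0.3-0.7) | 0.60 SD | 0.91 SD |
|---|---|---|
| Fallback reached | 51% (29-62%) | 17% (3-30%) |
| Mean fallback group term | 0.30 SD | 0.45 SD |
| 95% CI covers the 2-week effect | 80% (77-82%) | 61% (55-64%) |
| Power, interaction only | 49% | 84% |
| Power, either step | 59.7% | 90.1% |
| Power, ANCOVA | 60.0% | 91.8% |

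The GEE fits in step 3 gave a similar fallback rate at 0.60 SD (47.5%).

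**5. Two readings, kept apart.**
- Group term read as a drug effect, each step at 0.05: the null rejection rate over both steps is 9.6-10.1% per analyte (theory 1 − 0.95² = 9.75%), against 4.9-5.2% for one ANCOVA contrast. Power is then about equal, 59.7% against 60.0% at 0.60 SD.
- Group term not read as a drug effect: there is no inflation, but the only test of the drug is the interaction, at 49% against 60%.

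**6. Chance baseline difference.** One standard error is √(2/22) = 0.30 SD. With no drug effect the expected group term is (1+r)/2 × 0.30 = 0.23 SD for tissue and (1+2r)/3 × 0.30 = 0.20 SD for GCF. A baseline-adjusted contrast removes this.

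**The case against.** The strongest reply is that the plan assigns the test of the drug to the interaction and never says the fallback group term is a drug effect. The main-effects model may be meant only to report a pooled time effect. On that reading nothing is misestimated and one clarifying sentence would do. It is true that the documents do not settle the use, and the error-rate inflation depends on it. But they offer no other group estimate once the interaction is dropped, and nothing warns the reader off this one. The halving itself follows from the design under either reading.

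Several further points stand:
- The inflated error rate and the power gap belong to different readings and must not be added together. The gap reflects change scores against ANCOVA, not the fallback sentence.
- The fallback group test alone holds its 5% level under the null. With a one-standard-error baseline difference and no drug effect, it is significant in only about 1.6% of fallback trials at r = 0.5. An unadjusted 2-week comparison would itself carry 0.5 × 0.30 = 0.15 SD, so the excess is about 0.08 SD. Carry-over is the lesser harm.
- The plan promises no confidence intervals for these models, so the coverage figures apply only if such an interval is reported as the drug effect.
- Effect sizes and correlations are assumed, and the simulated power and error rates come from t-tests and ANCOVA rather than the planned GEE.
- These are secondary measures, already analysed.

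**Conclusion.** The concern holds and should be fixed. After a non-significant interaction, the group coefficient does not estimate the treatment effect. For tissue it is one half of the 2-week effect, whatever that effect or the correlation, given complete data and equal variances. For GCF with equal visit weights it is two thirds or one third, depending on whether the effect lasts, and less under AR(1). How often this matters depends on assumptions: the fallback is reached in about half of trials at 0.60 SD and about one in six at 0.91 SD (r = 0.5). A false-positive rate near 10% per analyte arises only if the group term is read as a drug effect. The interaction test and the primary CAL comparison are unaffected. Confidence is high for the dilution; how the term was used in reporting remains unknown.

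**What to change.** Remove the conditional fallback for the group comparison. For every log-transformed analyte and gene, report the baseline-adjusted group contrast with its 95% CI at 2 weeks, and also at 12 months for GCF, regardless of the interaction p-value. Either ANCOVA on the baseline value or a repeated-measures model with baseline means constrained equal across arms will serve. For GCF, apply the simulation-based adjustment already in the plan across the two visit contrasts, so that no second unadjusted test returns. A main-effects model may still be shown for the pooled time effect, with a sentence saying that a group term including baseline is not interpreted as a treatment effect.

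The cost is a re-run of completed models on existing data. The trial ran from March 2019 to December 2020 and the analyses are described in the past tense, so the results should be labelled post hoc. Some analytes now nominally significant may no longer be declared. ANCOVA drops patients who lack a baseline or follow-up sample; the constrained-baseline model keeps them.

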Each GCF sample containing two paper strips was eluted using 85 μ l of 1 \times PBS by gently agitating the samples on a rocker plate for 1 h at 4°C. Analyte concentrations were measured using magnetic bead panels (Millipore, Billerica, MA) and read on a MAGPIX with Luminex xPONENT software (Luminex Corporation, Austin, TX) per the manufacturers' recommendations.

Nine analytes were measured: Fibroblast growth factor (FGF-2), interleukin (IL)-1 β , IL-6, IL-10, IL-17A, insulin-like growth factor 1 (IGF-1), tumor necrosis factor (TNF)- α , receptor activator of nuclear factor kappa-B ligand (RANKL), and vascular endothelial growth factor A (VEGF-A). The amounts of cytokines are reported in picograms per ml, then mathematically adjusted by multiplying 0.085 to achieve pg per sample.

Analysis of interproximal tissue samples

Interproximal tissue samples were collected between the interproximal sulcus of the experimental site and adjacent tooth and were stored in 1.5 mL RNA/*later* solution (ThermoFisher Scientific, Waltham, MA). RNA extraction was conducted using the NucleoSpin RNA XS—complete kit for isolation and purification of total RNA from extremely small samples (Marcherey – Nagel, [Düren, Germany](#)). DNA digestion and cDNA synthesis were done using the QuantiTect Reverse Transcription Kit from QIAGEN© (Germantown, MD) per the manufacturers' recommendations.

Samples were diluted with water and placed in 96-well custom array plates in technical triplicate; qPCR was executed with SsoAdvanced Universal SYBR Green Supermix from Bio-Rad (Hercules, CA) reagents. PCR conditions were 39 cycles at 95°C for 3 minutes (1 cycle) 95°C for 15 seconds, and at 58°C for 30 seconds (39 cycles). At the end point of rt-PCR analysis, the threshold cycle

or $\Delta\Delta Ct$ values were recorded. To analyze the relative changes in gene expression, the $2^{\Delta\Delta Ct}$ method was done, as described by Livak et al (2001).

Statistical analyses

A sample size of 22 per group was needed to achieve at least 80% power to detect a difference of 1.0 mm in clinical attachment level between groups with a common estimated group standard deviation of 1.1 mm with a significance level of 0.05 using a two-sided two-sample t-test. This is based on mean data from most relevant previous studies (Killeen et al., 2012 and Jasa et al., 2019).

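### The between-group analysis of the primary outcome, CAL change, is not written out beyond the unadjusted t-test used for sizing, and baseline CAL is a covariate in no model

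*Combined protocol and SAP*

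**What the plan says.** All of this is in the Statistical analyses section of the combined protocol and SAP unless another section is named.

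- **Primary outcome.** "Clinical attachment level (CAL) change between baseline and 12-months was the primary clinical outcome measure for this clinical trial".
- **Definition.** "For change in CAL baseline CAL values were subtracted from 12 months CAL value", so a negative value is an improvement.
- **Stated use of that variable.** The "difference scores were plotted against GCF and rt-PCR measures at two weeks", and "Associations between change in CAL and measures at 2-weeks were assessed using Pearson correlations".
- **Sizing.** 22 per group is said to give 80% power or more; the target is "to detect a difference of 1.0 mm in clinical attachment level between groups with a common estimated group standard deviation of 1.1 mm". The test assumed there is an unadjusted t-test for two samples, two-sided at 5%.
- **GEE models.** For each measure of interest, "each model included the variables (analyte) group and time, as well as the interaction between group and time".
- **Change in BOP.** "logistic regression models were used, which included group and adjusted for worst side", with adjusted odds ratios and 95% confidence intervals.

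The Data Collection section has recession and probing depth, from which CAL is derived, recorded at baseline on six sites of the experimental and adjacent teeth. The Treatment Protocol section repeats the clinical measurements at 12 months.

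**The concern.** The plots and correlations set CAL change against biomarkers; neither compares simvastatin gel with control gel. The arm comparison that answers the trial's main question has to be inferred from the sizing sentence, while BOP change is given a named model, a covariate and an interval. The primary outcome is therefore specified less fully than BOP change.

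Baseline CAL is used only to form the difference score. A change score fixes the slope on baseline at 1, whereas ANCOVA estimates it. When the true slope differs from 1, the unadjusted comparison is less precise and a chance difference between arms at baseline carries into the estimated effect. At stake is precision in a trial of fifty patients, not the validity of the test.

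The text also leaves open whether 1.1 mm is the SD of CAL or of CAL change, and this decides whether the sizing matches the declared outcome.

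**Working it through.** **Inputs from the document.** Difference 1.0 mm, SD 1.1 mm, two-sided alpha 0.05, 22 per group, fifty patients.

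**Assumed, because the document gives neither.** r, the correlation of baseline with 12-month CAL: 0.3, 0.5, 0.7. k = SD(baseline)/SD(12 months): 0.7 to 1.0.

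**1. The plan's own figure.** Noncentral-t power with noncentrality 1.0/(1.1 × √(2/n)) and 2n - 2 degrees of freedom is 80.0% at n = 20 (79.997%), 82.0% at 21, 83.8% at 22 and 88.3% at 25. The stated 22 per group is consistent with at least 80% power.

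**2. Formulas.** With s1 the 12-month SD:

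- SD of change = s1 × √(1 + k² - 2rk)
- Residual SD under ANCOVA = s1 × √(1 - r²)
- Large-sample variance ratio, ANCOVA to change score = (1 - r²) / ((1 - r²) + (k - r)²)

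The ratio never exceeds 1 and equals 1 only at r = k. Examples: k = 1, r = 0.3 gives 0.91/(0.91 + 0.49) = 0.65; k = 0.7, r = 0.3 gives 0.91/(0.91 + 0.16) = 0.85; r = k = 0.7 gives 1. At r = k, estimating the slope costs about 1 point of power at 22 per group.

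**3. If 1.1 mm is the SD of change.** The t-test has 83.8% power. ANCOVA power by simulation (100,000 trials per cell, bivariate normal, common slope), with the difference from the t-test in points:

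| k | r = 0.3 | r = 0.5 | r = 0.7 |
|---|---|---|---|
| 1.0 | 95.1% (+11.1) | 91.8% (+7.9) | 88.3% (+4.5) |
| 0.85 | 91.9% (+7.9) | 88.0% (+4.2) | 84.4% (+0.7) |
| 0.7 | 88.3% (+4.5) | 84.7% (+0.8) | 82.7% (-1.0) |

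At k = 0.6, 0.5 or 0.3 the difference stays between -1.0 and +7.6 points. At 25 per group (fifty patients, equal split assumed) it runs from -0.7 to +8.9 across k = 0.7 and k = 1. Simulated type I error is 4.9-5.2% for both tests. The mean 95% CI half-width is 0.67 mm for the t-test and 0.54-0.67 mm for ANCOVA.

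**4. Chance imbalance, same reading.** A one-SE baseline difference moves the unadjusted contrast, relative to the adjusted one, by (r/k - 1) × SE. At k = 1, r = 0.3: s1 = 1.1/√1.4 = 0.93 mm, SE = 0.93 × √(2/22) = 0.28 mm, shift = -0.7 × 0.28 = -0.20 mm. Over k = 0.7 to 1.0 the SE is 0.22-0.43 mm and the shift 0 to 0.20 mm, in favour of the arm that started worse.

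**5. If 1.1 mm is instead the SD of 12-month CAL.** At k = 1, r = 0.3 the SD of change is 1.1 × √1.4 = 1.30 mm. Change-score t-test power at 22 per group and r = 0.3 is 70.2% (k = 1), 76.3% (k = 0.85) and 81.3% (k = 0.7), against about 86% for simulated ANCOVA. The largest SD giving 80% power is 1.157 mm, so the t-test falls short when r is below (1 + k² - (1.157/1.1)²)/(2k): 0.45 at k = 1, 0.36 at k = 0.85, 0.31 at k = 0.75. At r = 0.7 the two tests are within 2 points.

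**6. Could the GEE sentence cover CAL?** It directly follows the log-transformed GCF and RT-PCR data, labels its terms with the word analyte, and comes before CAL is introduced, so it most naturally means the biomarkers. If it did cover CAL, the group-by-time term would, with complete 12-month data, be the same unadjusted change contrast. Baseline CAL would be part of the repeated outcome, not a covariate. If a non-significant interaction were then dropped, as the section allows, the group main effect would average baseline with 12 months and would not estimate a difference in change.

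**The case against.** The strongest reply is that two points are joined here and only one comes straight from the text. The comparison is not written out, but the sizing sentence already gives test, alpha, sidedness and target difference, so one linking sentence would close the gap. Preferring ANCOVA to a valid, adequately sized change-score test is a choice between sound estimators. Its benefit is uncertain in size and even in sign, because neither r nor k is known. The 6-9 mm entry criterion points to k below 1, where gains are smaller over most of the range. The trial ran from March 2019 to December 2020 and the document is dated March 2022, so an ANCOVA added now cannot bring its power gain to the primary test. With CAL change as the declared outcome, 1.1 mm is most simply its SD, and the power figures below 80% need the other reading and a low r.

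Most of this stands as a limit on size. The t-test is valid, the gain may be nil, and timing decides the status of the ANCOVA. The direction of the imbalance shift also needs r no greater than k; with r = 0.7 and k of 0.6 or less it reverses. It is also true that the BOP model adjusts for worst side, not baseline, so it shows fuller specification and not a habit of baseline adjustment. None of this supplies a stated between-group analysis of the primary outcome or puts baseline CAL in a model. Nor is it unclear which baseline value to use: it is the one already subtracted to form the change score.

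**Conclusion.** The concern holds as a low-cost improvement, not as an error in the design. No between-group analysis of CAL change is written out beyond the sizing t-test, and baseline CAL enters no model. The 22 per group is sound if 1.1 mm is the SD of change. On that reading, adjustment is worth between -1 and +11 points of power and up to about 0.13 mm of CI half-width (0.67 - 0.54), and it removes a shift of up to 0.20 mm per SE of baseline imbalance. These ranges rest on assumed r of 0.3 to 0.7 and k of 0.7 to 1.0, bivariate normality and a common slope. The omission is certain; the size of the benefit is not. Recession is unrestricted at entry, so the pocket criterion alone cannot fix k.

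**What to change.** 1. State the between-group comparison of CAL change explicitly, giving the unadjusted mean difference with 95% CI and two-sided p from the two-sample t-test.
2. Beside it, report an ANCOVA of 12-month CAL (or CAL change; the treatment estimate is the same) on group and baseline CAL, using the baseline value that enters the change score. Give the adjusted mean difference, 95% CI and two-sided p.
3. Make the ANCOVA primary only if it can be shown to have been fixed before the data were seen. Otherwise keep the t-test as primary and label the ANCOVA as supportive and specified after data collection.
4. State whether 1.1 mm is the SD of CAL or of CAL change.

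The cost is wording and one model term on data already collected, with no new patients or visits. It uses one degree of freedom (42 to 41 at 22 per group) and costs about 1 point of power in the worst case, r = k.
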